#### **14.5.5 Neuropsychiatric events**

Neuropsychiatric events (in particular depression, anxiety and suicide ideation or behavior) will be tabulated separately based on the SMQ = ‘Depression and suicide/self-injury’. The SMQ search should include all TEAEs which code to a PT included in the Scope=Broad and/or Scope=Narrow groups within the SMQ.

#### **14.5.6 Inflammatory bowel disease**

Inflammatory bowel disease events will be tabulated separately, based on the HLTG = ‘Colitis excl infective’.

#### **14.5.7 Anaphylactic reaction**

Anaphylactic reactions will be summarized together in a stand-alone table with the following incidence rows:

- The first row within the body of the table will be labeled ‘Any hypersensitivity/anaphylactic reaction’ and will represent the overall incidence of subjects who reported at least one hypersensitivity reaction or at least one anaphylactic reaction
- The second row within the body of the table will be labeled ‘Any hypersensitivity reaction’ and will represent the overall incidence of subjects who reported at least one hypersensitivity reaction
- The third row within the body of the table will be labeled ‘Any anaphylactic reaction’ and will represent the overall incidence of subjects who reported at least one anaphylactic reaction

Following these three overall incidence rows, all TEAEs that have been identified as either a hypersensitivity reaction or an anaphylactic reaction will be summarized by SOC, HLT and PT (these will not be presented by subcategory).

Hypersensitivity reactions and anaphylactic reactions will be identified as follows:

- Hypersensitivity reactions: all TEAEs with onset (start date/time) within 24 hours after any administration of IMP, which code to a PT which contains the term ‘hypersensitivity’ will be considered as a hypersensitivity reaction and included in the summary table.
- Anaphylactic reactions: An algorithmic approach will be used to identify TEAEs that are considered to be anaphylactic reactions. Preferred terms are separated into 4 distinct categories (A, B, C, D) prior to the algorithmic approach being applied.

All TEAEs with onset (start date/time) within 24 hours after any administration of IMP, and which fulfill any of the 3 criteria described in [Section 14.5.7.1](#) will be included in the summary table.

Any TEAEs with missing start time will be assumed to have occurred at the time of or after dosing for this purpose, if the event date is on the same day as a dosing date.

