6.3.1 Potential drug-induced liver injury IMP discontinuation criteria

Subjects with potential drug-induced liver injury (PDILI) must be assessed to determine if IMP must be discontinued. In addition, all concomitant medications and herbal supplements that are not medically necessary should also be discontinued.

The PDILI criteria below require immediate discontinuation of IMP:

Subjects with either of the following:

- ALT or AST ≥ 5 ULN
- ALT or AST ≥ 3 xULN and coexisting total bilirubin ≥ 2 xULN
- Subjects with ALT or AST ≥ 3 xULN who exhibit temporally associated symptoms of hepatitis or hypersensitivity. Hepatitis symptoms include fatigue, nausea, vomiting, right upper quadrant pain or tenderness. Hypersensitivity symptoms include fever (without clear alternative cause), rash, or eosinophilia (ie, $>5\%$).

The PDILI criterion below allows for subjects to continue on IMP at the discretion of the Investigator.

- Subjects with ALT or AST ≥ 3 xULN (and ≥ 2 x Baseline) and <5 xULN, total bilirubin <2 xULN, and no eosinophilia (ie, $\leq 5\%$), with no fever, rash, or symptoms of hepatitis (eg, fatigue, nausea, vomiting, right upper quadrant pain or tenderness).

Evaluation of PDILI must be initiated as described in Section 12.6.1.

If subjects are unable to comply with the applicable monitoring schedule, IMP must be discontinued immediately.

Investigators should attempt to obtain information on subjects in the case of IMP discontinuation to complete the final evaluation. Subjects with PDILI should not be withdrawn from the study until investigation and monitoring are complete. All results of these evaluations and observations, as well as the reason(s) for IMP discontinuation and subject withdrawal (if applicable), must be recorded in the source documents. The eCRF must document the primary reason for IMP discontinuation.

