12.1.1.4 Adverse events for special monitoring

UCB has identified AEs for special monitoring (AESM). An AESM is an AE or safety topic for which special monitoring, additional data collection activities, and/or enhanced signal detection activities (within UCB), are considered appropriate. Identified AESM can be of particular concern based on findings from the IMP clinical program to date, potential risks generally associated with biologic immunomodulators, or comorbidities and risk factors prevalent in the study population.

Adverse events for special monitoring for this study include: infections (serious, opportunistic, fungal, and TB, see [Section 12.7.5](#)), neutropenia, hypersensitivity, suicidal ideation and behavior (assessed using the C-SSRS), depression, (assessed using the HADS, see [Section 9.10](#)), major cardiovascular events, liver function test changes/enzyme elevations (ALT, AST, and bilirubin; see [Section 12.6.1](#)), malignancies, and inflammatory bowel diseases (with gastroenterology referral as appropriate).

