##### **14.5.7.1 Anaphylactic reaction algorithm**

The SMQ = ‘anaphylactic reaction’ consists of 3 parts:

- A **narrow search** containing PTs that represent core anaphylactic reaction terms. If a subject reports any TEAE which codes to a PT included in Category A, then the event will be flagged as an anaphylactic reaction and summarized as such in the table
  - **Category A**

1. Anaphylactic reaction

2. Anaphylactic shock
3. Anaphylactic transfusion reaction
4. Anaphylactoid reaction
5. Anaphylactoid shock
6. Circulatory collapse
7. Dialysis membrane reaction
8. Kounis syndrome
9. Shock
10. Shock symptom
11. Type I hypersensitivity

- A **broad search:** If a subject reports any TEAE which codes to a PT included in Category B AND reports any TEAE which codes to a PT included in Category C, and both TEAEs have the same start date, then both events will be flagged as anaphylactic reactions and summarized as such in the table

– **Category B**

1. Acute respiratory failure
2. Asthma
3. Bronchial oedema
4. Bronchospasm
5. Cardio-respiratory distress
6. Chest discomfort
7. Choking
8. Choking sensation
9. Circumoral oedema
10. Cough
11. Cyanosis
12. Dyspnoea
13. Hyperventilation
14. Irregular breathing
15. Laryngeal dyspnea
16. Laryngeal oedema
17. Laryngospasm
18. Laryngotracheal oedema

This document cannot be used to support any marketing authorization and any extensions or variations thereof.

PUBLIC COPY

---

- 19. Mouth swelling
- 20. Nasal obstruction
- 21. Oedema mouth
- 22. Oropharyngeal spasm
- 23. Oropharyngeal swelling
- 24. Respiratory arrest
- 25. Respiratory distress
- 26. Respiratory dyskinesia
- 27. Respiratory failure
- 28. Reversible airways obstruction
- 29. Sensation of foreign body
- 30. Sneezing
- 31. Stridor
- 32. Swollen tongue
- 33. Tachypnoea
- 34. Throat tightness
- 35. Tongue oedema
- 36. Tracheal obstruction
- 37. Tracheal oedema
- 38. Upper airway obstruction
- 39. Wheezing
  - **Category C**
  - 1. Allergic oedema
  - 2. Angioedema
  - 3. Erythema
  - 4. Eye oedema
  - 5. Eye pruritis
  - 6. Eye swelling
  - 7. Eyelid oedema
  - 8. Face oedema
  - 9. Flushing
  - 10. Generalized erythema

This document cannot be used to support any marketing authorization  
PUBLIC COPY  
and any extensions or variations thereof.

11. Injection site urticarial
12. Lip oedema
13. Lip swelling
14. Nodular rash
15. Ocular hyperaemia
16. Oedema
17. Periorbital oedema
18. Pruritis
19. Pruritis allergic
20. Pruritis generalized
21. Rash

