22. Rash erythematous
23. Rash generalized
24. Rash pruritic
25. Skin swelling
26. Swelling
27. Swelling face
28. Urticaria
29. Urticaria popular

– **Category D**

1. Blood pressure decreased
2. Blood pressure diastolic decreased
3. Blood pressure systolic decreased
4. Cardiac arrest
5. Cardio-respiratory arrest
6. Cardiovascular insufficiency
7. Diastolic hypertension
8. Hypotension

- **An algorithmic approach:** If a subject reports any TEAE which codes to a PT included in Category D AND reports (either a TEAE which codes to a PT included in Category B OR a TEAE which codes to a PT included in Category C), and both TEAEs have the same start date, then both events will be flagged as anaphylactic reactions and summarized as such in the table.

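### The SAP's 'Any hypersensitivity reaction' row leaves out isolated urticaria, angioedema or rash, and every reaction starting more than 24 hours after a dose, and one Category D term can create a false anaphylaxis flag.

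*SAP*

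**What the plan says.** Protocol 12.1.1.4 lists the events for special monitoring. The list includes "neutropenia, hypersensitivity, suicidal ideation and behavior (assessed using the C-SSRS". It adds qualifiers to infections (serious, opportunistic, fungal, TB) but none to hypersensitivity.

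SAP 11.2 has one combined topic for hypersensitivity and anaphylactic reactions and refers to SAP 14.5 for the criteria. SAP 14.5.7 plans three incidence rows: either type of reaction, any hypersensitivity reaction, and any anaphylactic reaction.

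- **Hypersensitivity row.** It takes "all TEAEs with onset (start date/time) within 24 hours after any administration of IMP, which code to a PT which contains the term" 'hypersensitivity'. Such an event "will be considered as a hypersensitivity reaction and included in the summary table".
- **Anaphylaxis row.** It takes "All TEAEs with onset (start date/time) within 24 hours after any administration of IMP, and which fulfill any of the 3 criteria described in" SAP 14.5.7.1. Those criteria are a Category A term alone, a Category B term with a Category C term, or a Category D term with a Category B or C term. For the B and C pair, the rule is that a subject has a Category B event "AND reports any TEAE which codes to a PT included in Category C, and both TEAEs have the same start date". The Category D rule also requires a shared start date.

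Urticaria, angioedema, lip swelling and rash are all Category C terms. Category D includes "7. Diastolic hypertension".

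**The concern.** A 24-hour window suits acute anaphylaxis. Here it also governs a row labelled as any hypersensitivity reaction, together with a literal word match. An injected biologic can be followed by generalized urticaria or angioedema with no respiratory or circulatory sign, or by a rash some days later. If those events are coded under their own terms, the special-monitoring table does not show them. Someone who reads only that table could take a low or zero count as evidence that such reactions did not occur. Safety and tolerability of bimekizumab is the study's only secondary objective (Protocol 3.2), and the study plans at least 72 subjects (SAP 2.4), so a handful of events could decide whether the row reads zero.

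The Category D term works in the opposite direction. It can turn raised diastolic pressure plus a same-date rash into an anaphylaxis case.

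**Working it through.** The plan states no figure to reproduce. The check applies the written rules to the written term lists.

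**Inputs.** SAP 14.5.7 gives the 24-hour window, the word match and the treatment of missing start times. SAP 14.5.7.1 gives Category A (11 terms), B (39), C (29) and D (8). SAP 11.2 gives the TEAE period, from first dose to 140 days after the last dose.

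**Step 1: word match.** No term in Categories B, C or D contains 'hypersensitivity'. In Category A only 'Type I hypersensitivity' does.

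**Step 2: test cases.**

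| Event(s) and time after a dose | Hypersensitivity row | Anaphylaxis row |
|---|---|---|
| Each Category C term alone, 1 h (includes urticaria, angioedema, rash) | 0 of 29 | 0 of 29 |
| 'Hypersensitivity', 1 h | yes | no |
| 'Type I hypersensitivity', 1 h | yes | yes |
| 'Hypersensitivity', 25 h or 72 h | no | no |
| 'Anaphylactic reaction', 25 h or 72 h | no | no |
| Urticaria with wheezing, 1 h, same date | no | yes |
| Urticaria with hypotension, 1 h, same date | no | yes |
| Urticaria with wheezing, 30 h, same date | no | no |

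The missing-time rule treats an event on a dosing date with no start time as occurring at or after dosing. It does not bring in events on later days.

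**Step 3: is there another route?** SAP 11.2 points only to SAP 14.5, and neither document gives a second hypersensitivity search. Elsewhere in SAP 14.5, cardiovascular, malignancy, cytopenia, neuropsychiatric and hepatic events are found wholly or partly by standard MedDRA queries. Fungal infections and inflammatory bowel disease are found by MedDRA grouping terms. None of these has an onset window tied to dosing, and the SAP gives no reason for treating hypersensitivity differently.

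**Step 4: Category D.** The other seven terms are three for decreased blood pressure, hypotension, two arrest terms and cardiovascular insufficiency. 'Diastolic hypertension' points the other way. Under the D-plus-C rule, it and a same-date rash within 24 hours of a dose are both flagged as anaphylactic reactions. The lists also contain spelling slips ('Urticaria popular', 'Injection site urticarial', 'Pruritis'). If the program matches the SAP's text literally, those entries may fail to match coded terms.

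**The case against.** The strongest reply is that no event disappears. Isolated urticaria or a delayed rash still appears in the SAP 11.2 tables by SOC, HLT and PT, including those by intensity, relationship and seriousness. The AE listings show days since the most recent dose, so timing can be recovered. Incidence of AEs and SAEs, a primary safety variable, is unaffected, and the DMC reviews unblinded safety data under its own SAP. All of this stands. A reader might infer that these reactions go unreported. The documents do not support that: the gap is confined to the special-monitoring table and, presumably, the special-monitoring flag in the listings.

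Three other stronger readings also fail.

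- **The row will be near zero by construction.** No event rates are given. Protocol 12.1.2.1 also tells investigators to record the overall diagnosis instead of separate signs, so a reaction diagnosed as hypersensitivity within 24 hours would be caught. That instruction does not help when the recorded diagnosis is itself urticaria or angioedema.
- **The window's share of follow-up shows the share of events lost.** Six dosing visits in 84 days give 6/84 = 7.1% of the Treatment Period. Fifteen visits against 44 × 7 + 140 = 448 days give 15/448 = 3.3% of the full TEAE period. These are shares of calendar time. They would be shares of events only if onset were spread evenly over time, which the documents give no ground to assume.
- **The SAP breaks a protocol definition.** Protocol 12.1.1.4 names the topic but prescribes no search. Protocol 6.3.1 counts rash among hypersensitivity symptoms, but there it serves liver-injury discontinuation and does not define the special-monitoring event.

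A false case through Category D needs two specific same-date events within 24 hours of a dose. It is a remote possibility and adds little weight to the main point.

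**Conclusion.** The point holds for the special-monitoring table. Followed exactly, SAP 14.5.7 reports under a label of any hypersensitivity reaction only those TEAEs that start within 24 hours of a dose and carry that word in the preferred term. Lone Category C events reach none of the three rows (0 of 29), and nothing starting more than 24 hours after a dose is counted. The label therefore overstates what is counted for a topic the protocol names without limits of time or wording.

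The size in events is unknown and cannot be derived from the documents. The conclusion assumes that the rules are programmed as written and that no other hypersensitivity definition exists in documents not seen here, such as the DMC SAP. The primary efficacy analysis is untouched. This should be corrected, but it does not undermine the study's general safety reporting. The Category D entry is a separate list correction.

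**What to change.** In SAP 14.5.7:

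1. Define the hypersensitivity row by a pre-specified standard MedDRA query, for example the narrow-scope hypersensitivity SMQ in version 19.0 (the version named in SAP 3.8), over all TEAEs with no onset window. The documents do not list that query's contents, so the sponsor should confirm its scope before adopting it.
2. Show onset within 24 hours of dosing as a sub-row.
3. Keep the 24-hour algorithm for anaphylaxis only.
4. Check Categories A to D against the version 19.0 anaphylactic reaction SMQ, correcting 'Diastolic hypertension' and the misspelled terms.

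The cost is a SAP wording change and one program change. SAP Section 1 already provides for amendment when definitions change before database lock. The downside is that some unrelated allergic or skin events over the full TEAE period will be counted, in a number the documents do not allow one to estimate. The 24-hour sub-row separates out the acute reactions.

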##### **14.5.7.1 Anaphylactic reaction algorithm**

The SMQ = ‘anaphylactic reaction’ consists of 3 parts:

- A **narrow search** containing PTs that represent core anaphylactic reaction terms. If a subject reports any TEAE which codes to a PT included in Category A, then the event will be flagged as an anaphylactic reaction and summarized as such in the table
  - **Category A**

1. Anaphylactic reaction

2. Anaphylactic shock
3. Anaphylactic transfusion reaction
4. Anaphylactoid reaction
5. Anaphylactoid shock
6. Circulatory collapse
7. Dialysis membrane reaction
8. Kounis syndrome
9. Shock
10. Shock symptom
11. Type I hypersensitivity

- A **broad search:** If a subject reports any TEAE which codes to a PT included in Category B AND reports any TEAE which codes to a PT included in Category C, and both TEAEs have the same start date, then both events will be flagged as anaphylactic reactions and summarized as such in the table

– **Category B**

1. Acute respiratory failure
2. Asthma
3. Bronchial oedema
4. Bronchospasm
5. Cardio-respiratory distress
6. Chest discomfort
7. Choking
8. Choking sensation
9. Circumoral oedema
10. Cough
11. Cyanosis
12. Dyspnoea
13. Hyperventilation
14. Irregular breathing
15. Laryngeal dyspnea
16. Laryngeal oedema
17. Laryngospasm
18. Laryngotracheal oedema

This document cannot be used to support any marketing authorization and any extensions or variations thereof.

PUBLIC COPY

---

- 19. Mouth swelling
- 20. Nasal obstruction
- 21. Oedema mouth
- 22. Oropharyngeal spasm
- 23. Oropharyngeal swelling
- 24. Respiratory arrest
- 25. Respiratory distress
- 26. Respiratory dyskinesia
- 27. Respiratory failure
- 28. Reversible airways obstruction
- 29. Sensation of foreign body
- 30. Sneezing
- 31. Stridor
- 32. Swollen tongue
- 33. Tachypnoea
- 34. Throat tightness
- 35. Tongue oedema
- 36. Tracheal obstruction
- 37. Tracheal oedema
- 38. Upper airway obstruction
- 39. Wheezing
  - **Category C**
  - 1. Allergic oedema
  - 2. Angioedema
  - 3. Erythema
  - 4. Eye oedema
  - 5. Eye pruritis
  - 6. Eye swelling
  - 7. Eyelid oedema
  - 8. Face oedema
  - 9. Flushing
  - 10. Generalized erythema

This document cannot be used to support any marketing authorization  
PUBLIC COPY  
and any extensions or variations thereof.

11. Injection site urticarial
12. Lip oedema
13. Lip swelling
14. Nodular rash
15. Ocular hyperaemia
16. Oedema
17. Periorbital oedema
18. Pruritis
19. Pruritis allergic
20. Pruritis generalized
21. Rash
22. Rash erythematous
23. Rash generalized
24. Rash pruritic
25. Skin swelling
26. Swelling
27. Swelling face
28. Urticaria
29. Urticaria popular

– **Category D**

1. Blood pressure decreased
2. Blood pressure diastolic decreased
3. Blood pressure systolic decreased
4. Cardiac arrest
5. Cardio-respiratory arrest
6. Cardiovascular insufficiency
7. Diastolic hypertension
8. Hypotension

- **An algorithmic approach:** If a subject reports any TEAE which codes to a PT included in Category D AND reports (either a TEAE which codes to a PT included in Category B OR a TEAE which codes to a PT included in Category C), and both TEAEs have the same start date, then both events will be flagged as anaphylactic reactions and summarized as such in the table.

#### 14.5.8 Hepatic events and drug-induced liver injury

Hepatic events will include:

- Events based on the SMQ = 'Drug related hepatic disorders - comprehensive search' (excluding sub-SMQs = 'Liver neoplasms, benign [incl cysts and polyps]' and 'Liver neoplasms, malignant and unspecified'). All AEs should be included in the tabulation (including those considered both related and not related to the IMP) which code to a PT included in the Scope=Narrow group within each SMQ
- Hy's Law cases will also be summarized separately in a table of liver function abnormalities as described in [Section 11.3](#) (with adjudication for potential drug-induced liver injury [PDILI] cases)

#### 14.6 Treatment-emergent markedly abnormal laboratory values

The criteria for identifying TEMA laboratory values are provided for hematology in [Table 14-5](#) and for chemistry in [Table 14-6](#).

**Table 14-5: Definition of TEMA values for hematology**

Variable (SI units)	Source	Markedly abnormal definition			
		Low Grade 4	Low Grade 3	High Grade 3	High Grade 4
Hemoglobin (g/L)	RCTC	<70 OR decrease from Baseline of $\geq 30$	70 to <80 OR value <LLN and decrease from Baseline of 21 to 29	NA	NA
ALC ( $10^9/L$ )	CTCAE	<0.2	0.2 to <0.5	NA	NA
ANC ( $10^9/L$ )	RCTC	<0.5	0.5 to <1.0	NA	NA
WBC ( $10^9/L$ )	RCTC	<1.0	1.0 to <2.0	NA	NA
Platelets ( $10^9/L$ )	RCTC	<2.0	20 to <50	NA	NA

ALC=absolute lymphocyte count; ANC=absolute neutrophil count; CTCAE=Common Terminology Criteria for Adverse Events (CTCAE 2010); LLN=lower limit of normal; NA=not applicable; RCTC=Rheumatology Common Toxicity Criteria; WBC=white blood cell.

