6.3 Withdrawal criteria

Subjects are free to withdraw from the study at any time, without prejudice to their continued care.

Subjects should be withdrawn from the study and encouraged to come for the SFU Visit (20 weeks after the last received dose of IMP) if any of the following events occur:

1. Subject withdraws his/her consent.
2. The sponsor or a regulatory agency requests withdrawal of the subject.
3. There is confirmation of a pregnancy during the study, as evidenced by a positive pregnancy test.
4. Subject develops an illness that would interfere with his/her continued participation.

5. Subject considered as having either a suspected new LTBI or who develops active TB or NTMB infection during the study (including but not limited to, conversion demonstrated by interferon-gamma release assay [IGRA] or other diagnostic means) must be immediately discontinued from IMP, and an Early Withdrawal Visit must be scheduled as soon as possible, but not later than the next regular visit.

Confirmed active TB is a serious adverse event (SAE) and must be captured on an SAE Report Form and provided to the Sponsor in accordance with SAE reporting requirements.

As with all SAEs, periodic follow-up reports should be completed as per protocol requirements until such time as the TB infection resolves.

Additional information on TB policies are provided [Section 12.7.5](#).

6. Subject is noncompliant with the study procedures or medications in the opinion of the Investigator.

7. Subject uses prohibited concomitant medications as defined in this protocol (see [Section 7.8.2](#)) that may present a risk to the safety of the subject in the opinion of the Investigator and/or the Medical Monitor.

8. Subject develops laboratory abnormalities (with or without clinical symptoms) of ALT or AST as defined in Section [Section 6.3.1](#); neutropenia $<0.5 \times 10^9/L$; lymphopenia $<0.5 \times 10^9/L$. Any laboratory value or change judged to be clinically significant by the Investigator should prompt consideration of whether the subject should continue on IMP. For clarification, laboratory values that are markedly abnormal as per [Table 19-2](#) and [Table 19-3](#) will be flagged to the Investigator and to the medical monitor but do not trigger mandatory withdrawal unless listed above (Refer to [Section 6.3.1](#) for withdrawal criteria in relation to potential drug-induced liver injury [PDILI].)

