19 APPENDICES

19.1 Modified New York (mNY) Classification Criteria for AS

Table 19–1: Modified New York (mNY) Classification Criteria for AS

Diagnosis
1. Clinical criteria: 
a. Low back pain and stiffness for more than 3 months which improves with exercise, but is not relieved by restb. Limitation of motion of the lumbar spine in both the sagittal and frontal planes.c. Limitation of chest expansion relative to normal values corrected for age and sex.
2. Radiologic criterion: Sacroiliitis grade ≥ 2 bilaterally or grade 3 to 4 unilaterally
Grading
1. Definite ankylosing spondylitis if the radiologic criterion is associated with at least 1 clinical criterion

AS=ankylosing spondylitis; mNY=modified New York Criteria

Note: A second grading of “probably ankylosing spondylitis” is part of the modified NY criteria, but it is not applicable for this study. It is included here for completeness. The grading will be probable ankylosing spondylitis if 3 clinical criteria are present and the radiologic criterion is present without any signs or symptoms satisfying the clinical criteria (other causes of sacroiliitis should be considered).

19.2 Markedly abnormal laboratory values**Table 19–2: Definitions of markedly abnormal hematology values**

Parameter (SI units)	Markedly Abnormal Definition	
	Low	High
Hemoglobin (g/dL)	<LLN AND >2.0 decrease from baseline	N/A
Hemoglobin (g/dL)	<8.0	N/A
Leukocytes (total x 1000)	<2.0	N/A
Lymphocytes (x 1000)	<0.5	N/A
Neutrophils (x 1000)	<1.0	N/A
Platelets (x 1000)	<50	N/A

LLN=lower limit of normal; N/A = Not Applicable; SI=standard international

Data source: modified from Appendix Rheumatology Common Toxicity Criteria v.2.0 presented in Woodworth et al, 2007

^a Withdrawal criteria for neutrophils is <0.5 (Section 6.3)**Table 19–3: Definitions of markedly abnormal biochemistry values**

Parameter (SI units)	Markedly Abnormal Definition	
	Low	High
Alkaline Phosphatase	N/A	>3 x ULN
ALT	N/A	>3 x ULN
AST	N/A	>3 x ULN
Calcium (mg/dL)	<7.0	>12.5
Creatinine (mg/dL)	N/A	>1.8 x ULN
Glucose (mg/dL)	<40	>250
Potassium (mmol/L)	<3.0	>6.4
Sodium (mmol/L)	<125	N/A
Total bilirubin	N/A	≥2 x ULN
Uric acid	N/A	≥3 x ULN

ALT=alanine aminotransferase; AST=aspartate aminotransferase; N/A=Not applicable; SI=standard international; ULN=upper limit of normal

19.3 Protocol Amendment 1

Rationale for the amendment

The purpose of this protocol amendment is the following:

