### **11.3 Clinical laboratory evaluations**

Laboratory data (chemistry, hematology, and urinalysis) and changes from Baseline (if applicable) for numeric variables will be listed by treatment group and visit. Any laboratory variables that are BLQ or ALQ will be handled as described in [Section 4.2.3](#). Values outside the reference range for the numeric variables will be flagged in the listings and, in addition, will be listed separately. The reference ranges will also be reported in the listings.

Chemistry and hematology variables presented in [Table 11-1](#) will be summarized by treatment group at each visit, for both observed values and changes from Baseline. Figures of mean and mean change from Baseline will be presented by treatment for the absolute neutrophil count (ANC). All treatment groups will be overlaid on the same plot and the plot will include the error bars based on the SD (ie, mean +/-SD).

Laboratory variables will be grouped according to the laboratory function panel and categorized as normal, high or low, if applicable, based on the reference range supplied by the analytical laboratory. For selected variables that are identified in [Table 11-1](#), the change in category from Baseline will be presented in shift tables at all post-Baseline visits.

The number and percentage of subjects with treatment-emergent markedly abnormal (TEMA) values will be tabulated by treatment group and visit. Markedly abnormal laboratory values will generally be defined as those categorized as Grade 3 or Grade 4 as per the Rheumatology Common Toxicity Criteria (RCTC). Communication with the lead author of the RCTC publication has revealed that the reference ranges for absolute lymphocyte counts (ALC) are in error, therefore ALC criteria will follow the ranges defined as per the Common Terminology Criteria for Adverse Events (CTCAE) Version 4.03 (United States Department of Health and Human Services, 2010). Additional laboratory variables (not present in the RCTC publication) will also be categorized as per the CTCAE Version 4.03. The criteria for identifying TEMA values are presented in [Table 14-5](#) and [Table 14-6](#) for hematology and chemistry values respectively.

Laboratory measurements meeting the criteria for TEMA will be listed separately for hematology and chemistry. The listings will include all measurements for any variable with at least one TEMA result for each subject.

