**Table 14-6: Definition of TEMA values for chemistry**

Variable (SI units)	Source	Markedly abnormal definition			
		Low Grade 4	Low Grade 3	High Grade 3	High Grade 4
ALP (U/L)	RCTC	NA	NA	>3.0 to 5.0 x ULN	>5.0 x ULN
ALT (U/L)	RCTC	NA	NA	>3.0 to 8.0 x ULN	>8.0 x ULN
AST (U/L)	RCTC	NA	NA	>3.0 to 8.0 x ULN	>8.0 x ULN

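### The SAP's markedly abnormal laboratory criteria differ from the protocol's without explanation: an in-range hemoglobin can be Grade 4, and glucose and uric acid have no row

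*SAP*

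**What the plan says.** **Protocol, Section 19.2.** Table 19-2 treats hemoglobin as markedly abnormal if it is "<LLN AND >2.0 decrease from baseline" (in g/dL), or if it is under 8.0 g/dL. Table 19-3, "Definitions of markedly abnormal biochemistry values", covers ten analytes. Two of them are glucose (<40 or >250 mg/dL) and uric acid (≥3 x ULN). Each analyte has at most one limit in each direction, with no grades. Section 6.3 gives the use of these lists: "For clarification, laboratory values that are markedly abnormal as per" the two tables go to the Investigator and the medical monitor, but do not by themselves force withdrawal.

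**SAP, Section 11.3.** "Markedly abnormal laboratory values will generally be defined as those categorized as Grade 3 or Grade 4" of the Rheumatology Common Toxicity Criteria (RCTC). CTCAE 4.03 is used for lymphocytes and for variables that RCTC does not cover. "The criteria for identifying TEMA values are presented in" Tables 14-5 and 14-6. Subjects with treatment-emergent markedly abnormal (TEMA) values are tabulated by treatment group and visit, and their measurements are listed.

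**SAP, Table 14-5, hemoglobin (g/L, source given as RCTC).** Grade 3 is "70 to <80 OR value <LLN and decrease from Baseline of 21 to 29". Grade 4 is "<70 OR decrease from Baseline of" 30 or more, with no LLN condition.

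**SAP, Table 14-6, "Definition of TEMA values for chemistry".** The rows are ALP, ALT, AST, creatinine, GGT, potassium, sodium, total bilirubin, calcium and total cholesterol. There is no row for glucose or uric acid, although SAP Table 11-1 lists both as measured.

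**The concern.** One term has two definitions in one trial. The hemoglobin row is also uneven within the SAP: the more severe grade can be met by a value inside the normal range, while the less severe fall criterion cannot. In chemistry, two analytes that the protocol calls markedly abnormal have no route into the TEMA outputs.

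The SAP explains its grading elsewhere. It gives a reason for using CTCAE for lymphocytes, and a footnote gives the source of the high sodium limits. Neither Section 11.3 nor Section 3.9 (changes from the protocol-defined analyses) mentions the hemoglobin difference or the two missing analytes.

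Safety and tolerability of bimekizumab is the secondary objective. A glucose or uric acid value flagged to the Investigator under the protocol would be absent from the TEMA table. A hemoglobin value never flagged could appear there as Grade 4. The groups are small: 72 subjects at 2:1 is about 48 and 24, so one subject moves a percentage by 1/48 = 2.1 points or 1/24 = 4.2 points.

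**Working it through.** The plan states no figure to reproduce, so the check compares the two rule sets directly.

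**Units.** Protocol hemoglobin limits: 8.0 g/dL = 80 g/L, and 2.0 g/dL = 20 g/L. Protocol calcium limits: 7.0/4 = 1.75 and 12.5/4 = 3.125 mmol/L, as in the SAP.

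**Hemoglobin rules** (v = value, b = Baseline, in g/L):
- Protocol: v < 80, or (v < LLN and b − v > 20).
- SAP Grade 4: v < 70, or b − v ≥ 30.
- SAP Grade 3: 70 ≤ v < 80, or (v < LLN and 21 ≤ b − v ≤ 29).

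The documents give no LLN, so 115 to 135 g/L is assumed. Every whole-number pair with b from 85 to 185 and v from 50 to 185 was classified under both rules.

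| Assumed LLN (g/L) | Protocol only | SAP only | Lowest discordant Baseline (LLN + 30) |
|---|---|---|---|
| 115 | 0 | 861 | 145 |
| 120 | 0 | 666 | 150 |
| 130 | 0 | 351 | 160 |
| 135 | 0 | 231 | 165 |

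Every SAP-only pair has v ≥ LLN and b − v ≥ 30, and every one is Grade 4. The counts follow from k(k + 1)/2 with k = 156 − LLN; for LLN 130, 26 × 27/2 = 351. They are counts of grid cells and say nothing about how often subjects would fall there.

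**The step at 30 g/L**, with LLN 130:
- 160 to 131: fall 29, not below LLN. Not TEMA, and not markedly abnormal in the protocol.
- 160 to 130: fall 30, not below LLN. SAP Grade 4, and not markedly abnormal in the protocol.

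If v < LLN is also required for the Grade 4 fall, the SAP rule (Grade 3 or 4) and the protocol rule agree on every pair tested.

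**Chemistry rows.**
- In the protocol, not in the SAP: glucose and uric acid (2 of 10).
- In the SAP, not in the protocol: GGT and total cholesterol.
- Sodium: the low limit agrees; the SAP adds high limits where the protocol has none.
- ALP, ALT, AST, creatinine, potassium, total bilirubin and calcium: the outer limits agree after unit conversion.

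The platelet row of Table 14-5 has a separate inconsistency between its Grade 4 and Grade 3 limits (<2.0 against 20 to <50). It is not part of this point.

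**The case against.** The strongest reply is that the lists do different jobs. The protocol's stated use is flagging during the study, and its Section 15.8.1 plans only a descriptive presentation of laboratory values. No protocol-defined analysis uses Tables 19-2 or 19-3. A reader might infer that the SAP breaches the protocol or hides a change that Section 3.9 had to declare. The documents do not support that. What stands is an unexplained difference in one term, in two lists that both cite RCTC.

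Second, the SAP labels its hemoglobin row RCTC, whereas protocol Table 19-2 is described as modified from RCTC. The SAP may simply follow its source, which cannot be checked from these documents. It would therefore go too far to call the Grade 4 cell a proven error, or to say that adding the LLN condition is the only correct repair.

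Third, a reader might infer that glucose and uric acid drop out of the safety reporting. They do not. Under Section 11.3 both are summarized by visit, and out-of-range values are flagged and listed; the gap is confined to the TEMA table and listing. Nor is any Grade 3 or 4 count misreported for them, because the protocol gives them no grades. The general RCTC/CTCAE sentence in Section 11.3 could be read to reach them, but it supplies no limits and the two tables are named as the criteria.

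Fourth, the reach is modest. Laboratory change is an 'other' safety variable, the hemoglobin difference only adds cases relative to the protocol, and the SAP list is broader than the protocol's in places. All of this stands and limits the weight of the point. It does not remove the step at 30 g/L or the missing rows.

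**Conclusion.** The point holds as an unexplained inconsistency that should be reconciled. Followed as written, the TEMA tables can grade an in-range hemoglobin as 4 while a fall 1 g/L smaller is not counted at all. They also cannot count two of the ten chemistry analytes that the protocol calls markedly abnormal.

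The number of subjects affected cannot be computed, because neither the LLN nor the Baseline hemoglobin distribution is given. It is probably small: a discordant hemoglobin case needs a Baseline of at least LLN + 30, which is 145 to 165 g/L over the assumed LLN range. The agreement after repair assumes hemoglobin in whole g/L. The primary efficacy analysis and the protocol's in-study flagging are not affected.

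**What to change.** 1. Add glucose and uric acid to the TEMA tabulation and listing, with the protocol Table 19-3 limits as the markedly abnormal threshold and glucose converted to SI units. One ungraded category is enough, because the protocol gives no Grade 3/4 split.
2. Reconcile the hemoglobin Grade 4 fall with Grade 3 and protocol Table 19-2. Either require a value below LLN or, if the cited RCTC grade has no such condition, keep the cell, say so, and report falls of at least 30 g/L with a value at or above LLN on a separate line.
3. State the remaining differences in the SAP: GGT, total cholesterol and the high sodium limits.

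The cost is a few cells of SAP text, a unit conversion and slightly more programming, with no new data. The hemoglobin Grade 4 count may be lower if the LLN condition is added.
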